7.10.5.4 Overall Response Rate

Overall response rate is defined as the proportion of subjects who achieve a complete or partial response during the course of the study. The best response experienced by a subject (CR > PR > SD > PD) will be used. Responses will be determined by investigator review. The primary study endpoint will be use RECIST v. 1.1 definitions (sections 7.10.5.1 and 7.10.5.2) to define overall response rate. Overall response rate by iRECIST criteria (section 7.10.5.3) will be a secondary endpoint.

7.10.5.5 Duration of Response

Duration of Overall Response: The duration of overall response is measured from the time measurement criteria are met for CR or PR (whichever is first recorded) until the first date that recurrent or progressive disease is objectively documented (taking as reference for progressive disease the smallest measurements recorded since the treatment started).

The duration of overall CR is measured from the time measurement criteria are first met for CR until the first date that progressive disease is objectively documented.

Duration of stable disease: Stable disease is measured from the start of the treatment until the criteria for progression are met, taking as reference the smallest measurements recorded since the treatment started, including the baseline measurements.

7.10.6 Toxicity Evaluation

All subjects entered into the study and who are given at least one dose of abemaciclib will have detailed information collected on adverse events for the overall study safety analysis. All adverse events will be categorized and tabulated using CTCAE v. 5.0.

7.10.7 Progression-Free Survival

PFS is defined as the duration of time from start of treatment to time of progression using both RECIST v. 1.1 and iRECIST criteria [15], death, or last patient contact when progression-free. For patients who are progression-free, PFS will be censored at the most recent date which documents progression-free status (i.e., scan date or clinical visit date).

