5.7 Subject Compliance Monitoring

Subjects will be required to maintain a pill diary documenting adherence to twice daily oral administration of abemaciclib. Study medication bottles will be brought to study visits at the start of each 28-day cycle and study diaries will be reviewed at the start of each cycle.

6 Study Procedures

Table 6: Schedule of Study Procedures

All labs and study visits have a window of +/- 4 days. All imaging has a window of +/- 7 days

Study Phase	Screening	Cycle 1 (35 days)				Cycle 2+ (28 days)		End of Study Visit ²	Follow-up ³
Study Days	-28 to 0	1 8 15¹ 29¹				1 15¹			
Treatment									
Abemaciclib		X-----				X			
Nivolumab			X			X			
Tests and Procedures									
Informed Consent	X								
Review Inclusion/ Exclusion Criteria	X								
Demographics/Medical History	X								X ³
Physical Examination	X	X	X			X		X	
Vital Signs: BP, HR, RR	X	X	X			X		X	
Height	X								
Weight	X	X				X		X	
ECOG PS	X	X	X			X		X	
Concomitant Medications	X	X				X		X	
IP Compliance						X		X	
AE Assessment		X	X			X		X	
CBC with differential ⁴	X	X	X	X	X	X	X ⁴	X	
Serum Chemistries ⁵	X	X	X	X	X	X	X ⁵	X	
TSH	X					X		X	
PT/aPTT ⁶	X					X ⁶		X ⁶	
Serum Pregnancy Test ⁷	X	X				X		X	
AFP ⁸	X	X ⁸				X ⁸		X ⁸	
HIV Screening ⁹	X								
Hepatitis B/C Screening ¹⁰	X	X ¹⁰				X ¹⁰		X ¹⁰	
Disease Assessment (CT or MRI) ¹¹	X					X		X	
Research Correlates									
Blood sample (50cc) ¹²	X		X	X ¹²		X		X	

CONFIDENTIAL

This material is the property of the University of Pennsylvania.

Tumor biopsy ¹³	X		X					
----------------------------	---	--	---	--	--	--	--	--

¹ Lab visit only

² Should occur within 30 days of end of protocol therapy

³ Follow-up will be through review of the available medical record and/or phone calls every 6 months for up to 2 years

⁴ CBC with differential including hemoglobin, white blood count, absolute neutrophil count, and platelet count. CBC will be repeated on day 15 of cycle 2 but is required on day 15 of subsequent cycles only if hematologic toxicity \geq Grade 2 by CTCAE v 5.0

⁵ Serum chemistries including sodium (Na), potassium (K), chloride (Cl), bicarbonate (HCO3), blood urea nitrogen (BUN), creatinine (Cr), albumin, total bilirubin, AST, ALT, and alkaline phosphatase. Chemistries will be repeated on day 15 of cycle 2 but are required on day 15 of subsequent cycles only if hepatotoxicity \geq Grade 1 by CTCAE v 5.0 or other toxicity measured by the panel \geq Grade 2 by CTCAE v 5.0 are present on day 1 of that cycle.

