6.2.4 End of Study Visit (within 30 days of end of protocol therapy)

- Focused physical exam
- Vital signs and weight
- ECOG PS
- CBC with differential and platelet count and serum chemistries (Na, K, Cl, HCO₃, BUN, Cr, Ca, Alb, TBili, AST, ALT, ALP)
- TSH
- AFP (only if elevated at screening)
- Serum pregnancy test for beta HCG (for women of childbearing potential, defined in Appendix A)
- HBV DNA PCR if hepatitis B surface antigen or core antibody previously positive
- Review of concomitant medications
- Review of abemaciclib pill diary
- Return of unused abemaciclib pills
- AE assessment
- Blood draw (50cc) for correlative research studies (procedures described in laboratory manual)
- Disease assessment (CT or MRI) if not performed within prior 28 days

The end of study visit can be conducted during a scheduled office visit (such as to review scans demonstrating progression) or separately.

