6.2.5 Follow-Up Phase of the Study

All subjects will be followed for survival, disease status and new anti-cancer treatment information unless the subject requests to be withdrawn from follow-up or the study is terminated by the Principal Investigator. Follow-up information will be collected via telephone or subject medical records until death, loss to follow-up, or study termination by the Principal Investigator, whichever occurs first. Subjects will be followed every 6 months up for a maximum of 24 months from the end of protocol therapy. If the subject no longer wishes to be contacted but maintains his or her consent, the study staff may use a public information source (e.g. newspaper or electronic obituary, county records) to obtain information about survival status only as per local data protection laws and approval from the relevant ethics committee.

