6.2.6 Subject Withdrawal

Subjects may withdraw from the study at any time without impact to their care. They may also be discontinued from the study at the discretion of the Investigator for lack of adherence to intervention or study procedures or visit schedules or unacceptable toxicity of the therapy. The Investigator may also withdraw subjects who violate the study plan, or to protect the subject for reasons of safety or for administrative reasons. It will be documented whether or not each subject completes the clinical study. Subjects who withdraw early will have one final visit to collect investigational product and to follow up regarding adverse events.

If a subject permanently discontinues all study treatment for reasons other than disease progression, such as toxicity, the state of disease in terms of progression should be noted at this time point. Ideally formal

CONFIDENTIAL

imaging should occur at this point to document the state of disease. Alternatively, the previous scan should be used. Where possible scanning should continue as per normal practice (RECIST v1.1) until progression has been reached as per protocol or the subject has started other anti-cancer treatment. The date of progression of disease should be recorded in the eCRF. Further treatment is at the treating doctor's discretion.

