7.10 Disease Assessments

7.10.1 Antitumor Effect

For the purpose of this study, patients will be evaluated for response every 8 weeks by CT scan of the chest with or without contrast and triphasic (non-contrast, arterial phase contrast, venous phase contrast) CT scan and/or MRI of the abdomen with IV contrast (pelvis required only if disease documented in pelvis on baseline scan). MRI scans of the abdomen are preferred if the patient is eligible to have this done. The same imaging modality should be used throughout the study.

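### PFS censoring in Section 7.10.7 gives two different dates, neither requiring a scan, which biases PFS upward by an amount that depends on how many subjects stop scanning

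*Combined protocol and SAP*

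**What the plan says.** Section 7.10.7 measures PFS from start of treatment to progression under both RECIST 1.1 and iRECIST, "death, or last patient contact when progression-free". The next sentence, on subjects who are progression-free, says "PFS will be censored at the most recent date which documents progression-free status (i.e., scan date or clinical visit date".

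Other sections determine how far these dates can lie from a scan:

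- On treatment, Section 7.10.1 says "patients will be evaluated for response every 8 weeks by CT scan of the chest". Table 6 sets clinic visits on day 1 of each 28-day cycle from cycle 2.
- At the end of study visit, Section 6.2.4 lists "Disease assessment (CT or MRI) if not performed within prior 28 days".
- For subjects who stop all treatment without progression, Section 6.2.6 treats imaging at that point as ideal and allows the previous scan to be used instead. It adds "Where possible scanning should continue as per normal practice", until progression or the start of other anti-cancer treatment.
- After therapy, Section 6.2.5 says "Follow-up information will be collected via telephone or subject medical records until death", among other end points, and "Subjects will be followed every 6 months up for a maximum of 24 months from the end of protocol therapy". Disease status is among the items collected.

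Section 8.4 summarises PFS by Kaplan-Meier as a median with a 90% confidence interval.

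**The concern.** Progression is established on images, but the censoring date need not be an imaging date. Between the last scan and a later visit or contact, a subject remains in the risk set although progression could not have been detected. The Kaplan-Meier curve then falls too slowly and the median is too long.

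Some of this time arises by design. Scanning under Section 6.2.6 ends when other anti-cancer treatment starts, while disease-status follow-up continues for up to 24 months after therapy. Section 7.10.7 has no rule for new therapy. The final visit for early withdrawals in Sections 6.2.6 and 6.2.7 names no scan, yet it would count as a clinic visit.

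The trial has one arm, so no control group shares the bias. Because the two sentences disagree, the choice of date could also be left until the data are seen.

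**Working it through.** **The plan's own figures.** No PFS value is stated. Section 8.3 gives a precision for time-to-event variables: 21 events, with a 90% interval for the median about half the mean in width. On the log scale, 1.645/√21 = 0.359, so the limits are exp(−0.359) = 0.698 and exp(0.359) = 1.432 times the median. The width is 0.734 × median, and for an exponential the median is 0.693 × mean, so the width is 0.734 × 0.693 = 0.51 of the mean. This agrees. The stated 81% power for ORR also reproduces: 8 or more responses in 27 gives exact alpha 0.0977 and power 0.812.

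**One subject's censoring date.**

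- Scan interval: 8 weeks, or 8/4.35 = 1.84 months.
- Protocol clinic visit: nominally at most 28 days (4 weeks) after the last scan, half an interval.
- Six-monthly contact: about 26 weeks after the last scan, 26/8 = 3.25 intervals. Over 24 months it could reach about 104 weeks.

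**The median.** Assumed, because the documents do not give them: exponential progression with true median 4 or 6 months; a fraction q who stop treatment without progression and have no further scans; the share of progressions picked up at 6-monthly contact (none, half or all); median post-progression survival of 9 or 15 months. Taken from the documents: n = 27, first on-study scan at cycle 3 day 1 (35 + 28 = 63 days, week 9), then every 8 weeks. There were 1,500 simulated trials per scenario. The table gives the mean excess in the Kaplan-Meier median over last-scan censoring, in weeks, as a range over the scenarios run.

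| q | Clinic visit | Contact, none picked up | Contact, half | Contact, all |
|---|---|---|---|---|
| 10% | 0.5–0.6 | 1.3–1.7 | about 1.2 | 0.9–1.2 |
| 20% | 0.9–1.0 | 3–4 | 2.7 | 1.8–2.4 |
| 30% | 1.6–1.9 | 6–7 | 4.5–4.6 | 2.9–4.2 |
| 40% | 2.3–3.1 | 9–14 | 6.3–7.1 | 4.0–5.9 |
| 50% | 3.8–4.5 | about 17 | 9.0–9.9 | 4.5–7.2 |

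Dividing by 4.35 gives months. For q of 10% to 30%, clinic visits add 0.5/4.35 = 0.1 to 1.9/4.35 = 0.4 months, and contacts with no pick-up add 1.3/4.35 = 0.3 to 7/4.35 = 1.6 months. At 50%, clinic visits add up to 4.5/4.35 = 1.0 month. With no pick-up, the chance that a single 27-subject trial's median moves by more than 8 weeks is 1–3% (q = 10%), 6–9% (20%), 18–25% (30%) and 37–53% (40%).

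**A second model.** Here 3% to 6% of subjects per month stop scanning, and all are recorded as progression-free at a contact 6 months later. The mean median rises from 5.1 to 5.7–6.6 months (+0.6 to +1.5) for a true median of 4, and from 7.2 to 8.4–9.6 months (+1.2 to +2.4) for a true median of 6. Three of these four shifts are below 1.84 months. If half of progressions are picked up at the contact the shift is 0.6 to 1.3 months, and if all are, 0.5 to 0.9. A contact 1 month after scanning stops adds 0.2 to 0.4.

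**The alternative.** In the first model, last-scan censoring stays within about 0.1 month of the result with everyone fully scanned for q up to 30% (5.0 against 5.0 months; 7.1 against 7.0). At 50% the gap reaches about 0.4 months.

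**Scale.** With 21 events and a median of 5.0 months, the 90% interval is 5.0 × 0.698 = 3.5 to 5.0 × 1.432 = 7.2 months.

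**The case against.** The strongest reply is that the second sentence of Section 7.10.7 is the operative rule and names scans and clinic visits, not telephone contact. On that reading only the clinic-visit route remains, and it is small. The protocol also limits unscanned time through the end of study scan, continued scanning where possible and follow-up of disease status. Death is a PFS event, and every efficacy-evaluable subject must have a post-baseline scan (Sections 7.10.2 and 8.4.2). PFS is secondary and descriptive; the planned historical comparison concerns ORR only.

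Most of this stands, and it limits the size. It does not remove the defect. The first sentence still names last contact. The second does not confine clinic visits to protocol visits, and Table 6 allows follow-up by review of the medical record, so an outside visit months after the last scan could qualify. The scanning safeguards are conditional or end at new therapy.

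A reader might infer that median PFS could be inflated by far more than one scan interval. The documents do not support that. The 3.25-interval gap belongs to one subject's date. In the first model the median passes 8 weeks on average only through the contact route: with no pick-up, when roughly 35% to 40% or more stop without progression and are never scanned again, and with half picked up, only at about 50%. None of these rates is documented. A reader might also infer a planned test of PFS against historical values; there is none.

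**Conclusion.** The point holds as a defect in a stated rule. Section 7.10.7 gives two censoring dates, neither tied to a scan, for an endpoint defined by imaging, and the bias is upward. Under the assumptions shown, it is about 0.1 to 0.4 months through clinic visits if 10% to 30% stop scanning (about 1 month at 50%). Through 6-monthly contacts it is roughly 0.3 to 1.6 months if 10% to 30% stop and progression is never picked up before death. Larger shifts need extreme assumptions. Most of these shifts are modest beside an interval of 3.5 to 7.2 months, but they run in one direction and the interval does not reflect them. The primary ORR test and its 81% power are unaffected.

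**What to change.** In Section 7.10.7:

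- Censor subjects with neither progression nor death at the date of the last adequate tumour assessment, for both the RECIST 1.1 and the iRECIST versions of PFS, and say what counts as adequate.
- Delete last contact and clinic visit as primary censoring dates.
- For subjects who start new anti-cancer therapy without progression, apply the same rule, using the last adequate assessment before it began.
- Keep visit- or contact-date censoring as a sensitivity analysis. This is useful because last-scan censoring is not free of bias if subjects stop scanning when they are doing worse.

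How to treat progression or death after several missed scans is a separate choice that the section should also state.

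The cost is a change of wording. Scan dates are already collected and no visits or scans are added. The reported median PFS may be slightly shorter.

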7.10.8 Overall Survival

OS is defined as the duration of time from start of treatment to death due to any cause or last patient contact alive. Public records (e.g. obituaries) may be used to ascertain dates of death for subjects where such data is not available in the medical record unless the subject withdraws consent for follow-up. For subjects who enroll in hospice care in whom the specific date of death cannot be determined, date of death will be recorded as the date the patient entered hospice. In subjects who are alive or lost to follow-up, OS will be censored at last date of contact alive.

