8.3 Sample Size and Power Determination

Overall response rate to PD-1 therapy in HCC has varied in published studies from 15-20%. By combining available data from these studies, an overall response rate of 18% is estimated for PD-1 monotherapy. Doubling of this response rate, from 18% (H0) to at least 36% (H1) would be highly promising and worthy of additional study. With 27 subjects, a one-sided binomial test with alpha = 0.10 will have 81% power to detect an improvement in ORR from 18% (H0) to 36% (H1). For proportions, a sample of n=27 will provide 90% confidence intervals that are a maximum of 0.34 in width. For additional time to event variables, 27 subjects (21 events by 24 months) yields 90% confidence intervals for median survival that are approximately half of mean survival in width (assuming exponential survival).

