8.4 Statistical Methods

ORR and other binary variables will be analyzed using binomial exact tests, using a one-sided 10% type one error. Progression-free survival, duration of survival, and overall survival will be analyzed using Kaplan-Meier methods. PFS and DOR will be summarized as medians with 90% confidence intervals. Toxicity rates will be summarized as binomial proportions with 90% confidence intervals.

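### The hospice rule dates an undatable death at hospice entry, the earliest possible day, and does not say that death must first be confirmed

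*Combined protocol and SAP*

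**What the plan says.** Section 7.10.8 defines the endpoint: "OS is defined as the duration of time from start of treatment to death due to any cause or last patient contact alive". It then gives three rules for finding or replacing a date.

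- Other sources: "Public records (e.g. obituaries) may be used to ascertain dates of death for subjects where such data is not available in the medical record". This does not apply once consent for follow-up has been withdrawn.
- Hospice: for subjects who enrol in hospice "in whom the specific date of death cannot be determined, date of death will be recorded as the date the patient entered hospice".
- Censoring: "In subjects who are alive or lost to follow-up, OS will be censored at last date of contact alive".

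No order of precedence is given between the second and third rules.

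Section 6.2.5 sets the contact schedule: "Subjects will be followed every 6 months up for a maximum of 24 months from the end of protocol therapy". Section 7.10.7 ends PFS at progression, "death, or last patient contact when progression-free", so a death date can also enter PFS. On analysis, Section 8.4 says only that "Progression-free survival, duration of survival, and overall survival will be analyzed using Kaplan-Meier methods". Section 8 does not mention the hospice rule and plans no sensitivity analysis for it.

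**The concern.** There are two separate problems.

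The first is the date. Hospice entry is a day on which the subject was alive, so every use of the rule removes the whole interval from hospice entry to death. The errors all have the same sign and cannot average out. The rule makes no exception for later contact, so a subject recorded as alive at a 6-monthly call after entering hospice can still be dated as dead before that call.

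The second is who is covered. The sentence does not say that the subject must be known to have died. For a hospice subject who is then lost to follow-up, one analyst could record an event at hospice entry and another could censor at last contact alive. Both could cite Section 7.10.8.

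OS is a secondary endpoint with no planned test. However, the reference for the trial is historic nivolumab data, and Section 1.3.1 reports a median OS of 15.0 months from the dose-escalation part of the nivolumab study. Readers will probably set the two medians side by side.

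**Working it through.** **The plan's own figures.** Section 8.3 states that "With 27 subjects, a one-sided binomial test with alpha = 0.10 will have 81% power to detect an improvement in ORR". Declaring success at 8 or more responses in 27 gives an exact type I error of 0.0977 at 18% and power of 0.812 at 36%, so the stated figure reproduces. No death date enters this test.

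Section 8.3 also expects 21 events by 24 months and a 90% interval for the median about half of mean survival wide. For exponential survival with d = 21 events, as a fraction of the mean:

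- Wald: 2 × 1.645/√21 × ln 2 = 0.50
- Log scale: (e^0.359 − e^−0.359) × ln 2 = 0.51, where 0.359 = 1.645/√21
- Chi-square: 0.53

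This reproduces too.

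**Direction.** For an affected subject, recorded OS = true OS − g, where g is the time from hospice entry to death. Since g cannot be negative, the bias is downward only.

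**An illustration with assumed dates.** Months count from the end of therapy. The subject enters hospice at month 5, is alive at the month-6 call, and at the month-12 call is found to have died on an unknown day. The death lies between months 6 and 12. The current rule records month 5, which is 1 to 7 months too early and before a documented contact alive. The midpoint, month 9, is wrong by at most 3 months in either direction.

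**Size.** The documents give neither the share of deaths affected (f) nor g, so both are assumptions. With exponential survival, rate λ = ln 2/median and no censoring, the shift in the median is ln(1 − f + f·e^(−λg))/λ. Three median values have some basis in the documents:

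- 6.2 months: 21 of 27 events with uniform 18-month accrual plus 6 months of follow-up. Solving 1 − (e^(−6λ) − e^(−24λ))/(18λ) = 21/27 gives λ = 0.111.
- 11 months: 21 of 27 events with everyone followed for 24 months. λ = −ln(6/27)/24 = 0.0627.
- 15 months: the figure in Section 1.3.1.

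| Median | f = 10%, g = 0.5 | f = 30%, g = 3 | f = 40%, g = 2 | f = 40%, g = 3 | Half of mean survival |
|---|---|---|---|---|---|
| 6.2 | −0.05 | −0.80 | −0.75 | −1.08 | 4.5 |
| 11 | −0.05 | −0.84 | −0.77 | −1.13 | 7.9 |
| 15 | −0.05 | −0.86 | −0.78 | −1.15 | 10.8 |

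All entries other than f are in months. Half of mean survival is 0.5 × median/ln 2.

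A Kaplan-Meier simulation (27 subjects, 18-month accrual plus 6 months, f = 10-40%, g = 0.5-2) gives typical falls of 0.04-0.8 months at a 6.2-month median, 0.03-0.5 at 11 months and under 0.2 at 15 months. The falls are smaller at the longer medians because only deaths observed before the data cut are moved.

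**The opposite error.** In the same simulation, where every affected subject has in truth died, censoring those subjects at hospice entry raises the typical median by 0.6-3.8 months (6.2), by 1.0-7.6 months (11), and by 1.7 months up to not reached (15). Precision also falls: going from 21 events to 19, 17 or 15 widens the log-scale interval from 0.51 to 0.54, 0.57 or 0.61 of the mean.

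**The case against.** A reader might infer that the hospice sentence and the censoring sentence contradict each other outright. The documents do not support that. The words *specific date of death* most naturally describe a subject known to have died, with only the day missing. On that reading the next sentence, which covers subjects alive or lost to follow-up, concerns different people. What stands is an ambiguity for hospice subjects lost to follow-up, because confirmation of death is not stated. The early dating of known deaths stands on either reading.

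The rule is also a last resort, used only after the medical record and public records fail to give a date, so the affected group may be very small. The upper assumptions are generous: 30% of 21 events is about 6 deaths with no findable date. The error understates OS, so it cannot create a false signal of benefit, and no test or comparator rests on OS. These points stand, and they limit the weight of the concern.

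Midpoint dating has its own error of up to 3 months under 6-monthly contact, and it will tend to be late if death usually follows soon after hospice entry. Censoring unconfirmed cases can bias OS upward by more than the current rule biases it downward. Both points stand and shape the fix.

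**Conclusion.** The concern holds in limited form. As written, the rule assigns a date that can only be too early and that can precede a documented contact alive. It also leaves unclear whether death must be confirmed.

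Under the assumed ranges, median OS falls by less than 1 month in most scenarios and by about 1.1 months in the corner where 40% of deaths are affected by 3 months each. At a 12-month median, half of mean survival is 0.5 × 12/ln 2 = 8.7 months. A fall of 0.85 months (30% affected, 3 months) is then about 10% of the interval width. The least favourable corner, at a 6.2-month median, is 1.08/4.5, or about a quarter of the width. These sizes rest on exponential survival and on hospice inputs that the documents do not give.

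The response-rate test and its 81% power are untouched. A reader might infer that the trial's conclusion is at risk, but nothing in Section 8 ties that conclusion to OS.

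**What to change.** Amend Section 7.10.8, and refer to it from Section 7.10.7 so that deaths counted in PFS are dated in the same way:

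1. Apply the imputation only to subjects confirmed to have died.
2. Never date a death before the last date the subject was known to be alive.
3. For a confirmed death on an unknown day, use the midpoint between the last date known alive and the first date known dead.
4. State that hospice subjects without confirmed death follow the existing censoring sentence.
5. Add to Section 8.4 a sensitivity analysis that counts the subjects in item 4 as deaths at hospice entry, as the current rule can be read to do. Present it as a lower bound, because the censoring in item 4 is probably informative and may bias OS upward.

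If hospice records are to count as confirmation, name them. Section 6.2.5 lists telephone, medical records and public sources, and Section 7.10.8 lists the medical record and public records. Neither names a hospice.

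The cost is a few sentences and one extra analysis, with no change to sample size, visits or treatment. The downside is that a few subjects may become censored and the OS interval widens slightly. For example, losing 2 of 21 events takes it from 0.51 to 0.54 of the mean. The wording should be settled before OS data are reviewed, so that the choice of reading is not made after the fact.
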